2.1 Study Rationale

New treatments for patients with high-grade brain cancers are urgently needed as currently available treatment options are scarce and offer only limited benefit to patients. Most anti-cancer drugs are unable to cross the blood-brain barrier (BBB) to reach therapeutic concentrations in the target tissue. The liposomal formulation possesses promising properties that make clinically meaningful delivery across the BBB a real possibility. Curcumin has shown encouraging activity in preclinical cancer models, including in gliomas, especially in combination with cytotoxic drugs.

A full nonclinical safety assessment has been completed for LC. Liposomal curcumin has been shown to be safe and efficacious in animals. The pharmacokinetics (PK), absorption, distribution, metabolism, and excretion (ADME) and toxicology data have not revealed any issues of concern to keep from starting first-in-human (FIH) studies with normal volunteers, as long as potential hemolysis is carefully monitored. A maximum recommended safe starting dose (MRSD) of 10mg/m² has been established to ensure a safe and well-controlled Phase 1 clinical trial.

We will pursue a Phase 1 dose-escalation study to assess the maximum tolerated dose (MTD) of LC, in combination with standard RT and TMZ in patients with newly diagnosed HGG, for which the standard of care is 6 weeks of RT with concomitant TMZ,

followed by adjuvant TMZ chemotherapy. The study will also assess the toxicity and feasibility of weekly administration of LC in combination with standard therapy, which will provide important information as a basis for design of a future efficacy trial.

2.2 Background

Administration of LC has been tested in a Phase 1a and a Phase 1b study in cancer patients (Greil et al, 2018). The RP2D of LC for weekly administration has been established at 300 mg/m² intravenously (IV).

Initial clinical data show an early drop in plasma levels of LC after discontinuation of IV infusion (Storka et al, 2015); however, drug accumulated at high levels in polymorphonuclear cells and was still detectable several hours after injection. Preclinical data in rat brain show encouraging drug levels in different areas of the normal brain, suggesting that LC can cross the BBB (Chiu et al, 2011).

2.2.1 Efficacy and Safety Pharmacology

Curcumin has been shown to modulate multiple cell signaling pathways and interact with numerous molecular targets, including cell cycle, apoptosis, proliferation, survival, invasion, angiogenesis, metastasis, and inflammation (Goel et al, 2008). Given its ability to affect multiple targets it is believed to have the potential to act against a large number of cancers, inflammatory diseases, parasitic diseases such as malaria, neurodegenerative diseases, arthritic degenerative conditions, cystic fibrosis, and diabetes.

Liposomal curcumin induced a dose-dependent inhibition of in vitro cell growth at concentrations of 2.5 to 100 µM in 6 pancreatic, and 2 colorectal cancer cell lines (Li et al, 2005; Li et al, 2007). Liposomal curcumin inhibited in vivo tumor growth in 2 xenograft mouse models of human pancreatic cancer (Li et al, 2005). It was shown that 20 mg/kg was the minimum effective dose. This is equivalent to 60 mg/m². A dosing regimen experiment showed that three times a week (TIW) dosing was the optimal dosing schedule for tumor growth suppression.

During the safety pharmacology evaluation of LC, the curcumin drug substance alone was shown to have inhibitory effects on the human ether-à-go-go (hERG) ion channel with a half-maximal inhibitory concentration (IC₅₀) of 4.9 µM (1800 ng/mL). When the LC drug product was tested, even at the highest concentration tested (11.4 µM; 4200 ng/mL) a 50% inhibition of hERG was not attained. Therefore, for LC, the IC₅₀ is above the maximum plasma concentration (C_{max}) thus far observed in the Phase 1 trial. Although there was a signal for inhibition of hERG in vitro at very high concentrations, no effects on electrocardiograms (ECGs) were seen in the dog 4-week toxicity study at doses up to 20 mg/kg (400 mg/m²). No effects of LC were seen on respiratory or neurological endpoints in the dog 4-week toxicity study.

2.2.2 Pharmacokinetics

The cytochrome P450 (CYP450) studies show no tendency for inhibition or induction of the common CYP450 drug metabolism enzymes, and, therefore, it is not expected that

LC will have major drug-drug interactions. Tetrahydrocurcumin (THC) is a major metabolite that is detected in plasma at high levels. Tissue distribution data obtained in a dog study after 2-hr and 8-hr continuous infusion revealed that 8-hr infusion yields lower concentrations of curcumin and THC in plasma but higher concentrations in target tissues than a 2-hr infusion.

2.2.3 Toxicology

Liposomal curcumin was tested in the in vitro *Salmonella typhimurium* (Ames) assay, and the in vivo mouse micronucleus assay. There were no signals for mutagenic potential from either of these studies.

Rat and a dog 4-week toxicity studies were done. The rats were given IV bolus injections TIW (empty liposomes, and 10, 20 and 40 mg/kg LC). The dogs were given IV infusions at 10 mL/kg/h for 1 h TIW (5% dextrose in water, empty liposomes, and 5 and 20 mg/kg LC).

For the rats, there were no deaths on the study, and no clinical signs. There were no effects on body weight, food consumption, clinical chemistries or organ weights, and no treatment-related effects on gross or microscopic pathology. Red blood cell (RBC) parameters began to decrease for all groups, including the empty liposomes group, with a nadir during Week 2. During Weeks 3 and 4 the RBC parameters began to improve, and 96 hr after the last dose, the parameters were approaching the normal range. Treatment with empty liposomes had the least effect, with a dose-response effect of the LC. Because the effects on the RBCs were minimal with no other adverse effects, the no observed adverse effect level (NOAEL) for the rat was considered to be > 40 mg/kg.

For the dogs treated with 5 mg/kg LC, the analysis of all generated data including clinical observations, ophthalmology, ECGs, clinical pathology, gross necropsy, and histopathology revealed no treatment-related toxicity.

In dogs dosed with empty liposomes during the first infusion, starting within 15-30 minutes of infusion, most animals started showing clinical signs that included lacrimation, labored breathing that progressed into passivity, weakness, and lethargy. During this period, pulse was weak and blood pressure was undetectable (hypotension). These symptoms were transient and lasted for about 20-30 minutes, after which animals started recovering. By the end of the infusion period and/or immediately after the infusion, all dogs recovered. During the subsequent dosing, these symptoms were present in most animals; however, they were of lesser intensity, as if the animals were adapting to the dosing. (Also, in 1 dog dosed with LC at 20 mg/kg on a few occasions during the infusions, there was angioneurotic edema [swollen face, eyelids, lips] and urticaria noted.) This anaphylactoid reaction is common after infusion with liposomes and was not unexpected (Szebeni et al, 2007). It should be noted that this hypersensitivity reaction occurred in all dogs infused with empty liposomes and in only 1 animal dosed with LC at 20 mg/kg. No animals in the group infused with LC at 5 mg/kg were affected. Pretreatment with an antihistamine and a corticosteroid will be performed in the Phase 1 clinical trial, as is usually done with infusion of liposomes. Pretreatment was not included

in this Good Laboratory Practice (GLP) dog toxicity study as to not interfere with the safety assessment of the LC.

For the dogs treated with the high dose of 20 mg/kg group, 2 animals died after the third dose. All animals in this group showed clinical signs of anorexia, significant weight loss, hematuria (3+), pale mucosal membranes, and intravascular hemolysis resulting in severe anemia. This severe hemolysis was seen at 6 hr and 24 hr after end of infusion. This was reflected in decreased RBC counts, hematocrit, hemoglobin (Hgb); and hematuria. Because of the severe hemolysis, the dose was lowered from 20 mg/kg to 10 mg/kg. After the dose was lowered to 10 mg/kg, the decreased RBC parameters in these dogs began to recover even while still being dosed at 10 mg/kg. The RBC parameters continued to improve during the 4-week recovery period. Reticulocytes increased very significantly after the second dose of 20 mg/kg. When the dose was lowered from 20 to 10 mg/kg, reticulocytes recovered significantly, and reached the normal range during the recovery period. Clinical chemistry findings included increases in total bilirubin, phosphorus, lactate dehydrogenase (LDH), and cholesterol.

In vitro hemolytic potential studies were done with both curcumin drug substance and LC. For dogs, hemolysis was seen at the two highest concentrations of LC (27% and 4% hemolysis [3200 and 1600 µg/mL, respectively]). For the human, hemolysis was only observed at the highest concentration (21% hemolysis at 3200 µg/mL). This concentration is 1200-fold the highest C_{max} seen in humans given the highest dose of 400 mg/m².

Since (1) the hemolysis began to reverse after changing the high dose from 20 to 10 mg/kg, (2) hemolysis can be easily monitored in the Phase 1 trials, and (3) there were no effects at 5 mg/kg, it was proposed that a 1/10 safety factor be applied for calculation of the MRSD for the Phase 1 trial. A 5 mg/kg dose in the dog is equivalent to 100 mg/m². With a safety factor of 1/10, the MRSD for the Phase 1 trial was 10 mg/m².

In vitro formation of echinocytes was investigated in ethylenediaminetetraacetic acid (EDTA) blood from two healthy donors incubated with 1 µg/mL, 10 µg/mL, or 100 µg/mL LC at 37°C. At 1 µg/mL, no effect on erythrocytes was observed. At 10 µg/mL and 100 µg/mL, erythrocytes changed from their normal biconcave shape and became spherical and spiked. The peak effect was already detectable at 30 minutes and lasted for the observation period of 4 hr.

Upon incubation with curcumin drug substance dissolved in dimethyl sulfoxide (DMSO) again, at a threshold dose of 10 µg/mL curcumin, erythrocytes changed their shape and became spherical and spiked after an incubation period of 30 minutes. This shape change normalized between 120 and 240 minutes.

When incubated with empty liposomes, the erythrocytes exhibited shape change after 240 minutes at a lipid concentration corresponding to 10 µg/mL LC. Compared to LC, a change in the shape of the RBCs was seen at the same concentration, but the time point of occurrence was delayed. Incubation with sample buffer or 0.99% DMSO did not influence the morphology of the RBC over 4 hr (Storka et al, 2013).

2.2.4 Clinical Studies

2.2.4.1 Phase 1a Study in Healthy Patients (LipoCurc 1001)

An FIH safety and PK study in healthy patients was conducted at the Medical University in Vienna (Principal Investigator [name]) between August 2011 and October 2012. Eligible male or female healthy patients were allocated to ascending dose groups starting with the lowest dose and randomized to receive either LC or placebo.

The originally planned dose groups were 10, 20, 40, 80, 120, and 180 mg/m² LC suspended in 5% glucose in a total of 500 mL water, and patients received IV premedication with dexamethasone 4 mg and diphenhydramine 30 mg diluted in 100 mL NaCl. Given the excellent tolerability, and following a protocol amendment, another set of patients were recruited to the dose levels 180, 240, 320, and 400 mg/m² with premedication with diphenhydramine alone.

The systemic safety of LC was good over the dose range between 10 and 320 mg/m². In patients dosed at 400 mg/m², an increase in mean corpuscular volume (MCV) and erythrocyte echinocyte formation in peripheral venous blood were observed and led to dose de-escalation and additional safety analyses. Minor decreases of erythrocytes and Hgb were observed in the 2 patients, but were judged as not clinically significant by the investigator. Markers of hemolysis (hydroxybutyrate dehydrogenase [HBDH], potassium, haptoglobin, LDH, erythrocytes, and Hgb) did not change significantly.

Blood smears prepared after dose de-escalation revealed transient shape changes of erythrocytes occurring at all investigated dose levels between 120 and 400 mg/m² (see Investigator's Brochure), which were not connected to clinical symptoms. For patients dosed with 120 mg/m², the process had a later onset and presumably only less severe changes were induced in the erythrocyte membrane. Eight patients were treated at 120 mg/m². Investigation of MCV, the parameter that triggered the preparation of blood smears, showed no change in the median MCV values (change between baseline and highest value < 1 fL) at 120 mg/m², whereas the median change of MCV for doses 180-400 mg/m² was between 4 and 13 fL.

In light of complete absence of clinical symptoms or clinically relevant changes in laboratory safety parameters, administration of 120 mg/m² LC over 24 hr using a continuous infusion pump seemed to be a safe and well-tolerated starting dose for clinical studies in cancer patients. However, the study was temporarily interrupted after 2 infusions in the first patient due to precipitate formation in the infusion line, most likely caused by shear forces and increased temperature at the pump head. The patient did not experience any adverse events (AEs) related to this incident. Based on the results of subsequent in-use stability tests and a decision by the Data and Safety Monitoring Board (DSMB), the study was continued by administering LC over 8 hr as a gravity infusion (without an infusion pump). As a reduced infusion time increases the concentration of LC over the time, the starting dose was reduced from 120 mg/m² to 100 mg/m². Gravity infusion (without an infusion pump) will be used throughout the clinical trial. The administration system via the syringe pump was tested in compatibility studies and the

stability of LC was demonstrated for 12 hr of perfusion and an extended observation period of 24 hr.

Infusion of LC resulted in rapid and dose-dependent development of plasma levels of curcumin and its metabolite THC with time to maximum plasma concentration (T_{max}) values ranging from 0.9-1.7 hr for curcumin and 0.5-1.8 hr for THC. C_{max} ranged between 42 ± 22 and 2359 ± 412 ng/mL for doses between 10 and 400 mg/m², respectively. The plasma levels of curcumin during infusion were 7- to 16-fold higher than those of THC. The clearance of curcumin was similar across doses and ranged from 1.42-5.29 L/kg/hr. Steady-state volumes of distribution were variable with dose and ranged from 0.34-19.97 L/kg.

The study results support the conclusion that the test medication LC, when administered IV, will achieve relevant plasma levels (ng/mL), indicating good systemic availability. Upon termination of infusion, the plasma levels dropped very rapidly for curcumin and THC, with mean residence times over a dose range of 120–400 mg/m² ranging from 0.18-0.62 hr for curcumin and 0.58-1.69 hr for THC. The postinfusion plasma exposure of curcumin was 4% to 10% of exposure during infusion, while the postinfusion plasma exposure of THC was 26% to 37% of the exposure during infusion.

Urinary clearance calculated from urine curcumin levels and urine volumes account for only a very small percentage (0.12%) of the total systemic clearance of curcumin in humans, consistent with studies in other species.

2.3 Benefit/Risk Assessment

High-grade gliomas carry a most dismal prognosis. Even after gross total resection followed by RT and TMZ, the median survival is poor. New therapies are clearly needed for this devastating disease.

Turmeric is well tolerated and is believed to have the potential to act against a large number of cancers by promoting death pathways and limiting survival pathways in tumor cells (Khor et al, 2006).

More detailed information about the known and expected benefits and risks and reasonably expected AEs associated with LC may be found in the Investigator's Brochure.

3 OBJECTIVES AND ENDPOINTS

Table 3. Objectives and Endpoints

Objective	Endpoint
Primary	

 To determine the MTD/RP2D of LC in combination with RT and TMZ and adjuvant TMZ in newly diagnosed HGG To determine the safety and tolerability of LC infused IV over 3 hr 	
 Number of observed DLTs (as defined in Section 4.1.1)
Secondary	

 To estimate safety and tolerability of LC in combination with standard RT/TMZ and adjuvant TMZ To determine feasibility of weekly LC infusion as defined as patients being able to complete 80% of the planned doses of LC, 80% of RT and 60% of TMZ within the first 10 weeks of treatment To assess efficacy 	
 Safety assessments include SAEs, AEs, findings on physical examination, clinical laboratory findings, and ECGs Proportion of patients at each dose level who receive at least 80% of the planned infusions of LC 80% of RT and 60% of TMZ within the first 10 weeks of treatment OS and PFS at each dose level, PFS based on RANO criteria

AE = adverse event; DLT = dose-limiting toxicity; ECG = electrocardiography; HGG = high-grade glioma; IV = intravenously; LC = liposomal curcumin; MTD = maximum tolerated dose; OS = overall survival; PFS = progression-free survival; RP2D = recommended phase 2 dose; RANO = Response Assessment in Neuro-Oncology; RT = radiation therapy; SAE = serious adverse event; TMZ = temozolomide

4.1.1 Dose-Limiting Toxicities

The DLT assessment period for this study is 10 weeks: 6 weeks of concurrent LC and CRT, and 4 weeks of single-agent LC.

Hematological Toxicities

Hematological toxicities will be considered dose limiting if any of the following occur and complete blood counts (CBCs) and differentials were obtained according to the mandated schedule (CBC, differential, and platelet count drawn twice a week until the ANC \geq 1500/ μ L and platelet count \geq 100,000/ μ L):

- ANC < 500/ μ L
- Platelet count < 25,000/ μ L
- Grade 4 anemia
- Grade 3 hemolysis
- Febrile neutropenia
- Any hematological toxicity that prevents administration of \geq 80% of the planned LC dose

Grade 3 or 4 lymphopenia will not be considered a DLT.

Central Nervous System Toxicities

Central nervous system (CNS) toxicities are:

- \geq Grade 2 CNS ischemia

- \geq Grade 2 neurological toxicities that interfere with activities of daily living and do not resolve spontaneously or with steroids, anticonvulsants, or electrolyte correction within 2 weeks
- Symptomatic CNS hemorrhage of any grade

Nonhematological, Non-CNS Toxicities

Grade 3 and 4 nonhematological, non-CNS toxicities will be considered DLTs, with the following exceptions:

- Grade 3 nausea, vomiting, or diarrhea despite sufficient prophylaxis with a duration < 3 days
- Alopecia
- Grade 3 fatigue
- Grade 3 hyperglycemia that is reversible and without clinical symptoms
- Grade 3 electrolyte disturbances that are asymptomatic and reversible within 3 days, and do not re-occur upon continuing or re-initiation at the same dose
- Grade 3 or 4 hypophosphatemia, unless considered clinically relevant
- Grade 3 or 4 elevations in alkaline phosphatase
- Grade 3 hypertension that resolved to \leq Grade 2 hypertension within 1 week either spontaneously or upon implementation of antihypertensive therapy
- A first episode of deep venous thrombosis (DVT) or pulmonary embolism

Hepatic DLTs are:

- ALT or AST > 8 *upper limit of normal (ULN), regardless of duration
- ALT or AST > 5 *ULN and ≤ 8 *ULN that fails to return to \leq Grade 1 within 2 weeks despite medical intervention
- Total bilirubin > 5 *ULN
- ALT or AST > 3 *ULN and concurrent total bilirubin > 2 *ULN

FOR PATIENTS ON CONCURRENT TREATMENT, ANY DLT (AS DEFINED ABOVE) CAUSING DELAY IN TREATMENT OF OVER 7 DAYS WITHOUT RECOVERY TO A \leq GRADE 1 OR BASELINE STATUS WOULD RESULT IN TAKING THE PATIENT OFF CONCURRENT TREATMENT.

FOR PATIENTS RECEIVING ADJUVANT TREATMENT, ANY AE (AS DEFINED ABOVE FOR DLT) CAUSING DELAY IN TREATMENT OF OVER 14 DAYS (POST CYCLE 1 DAY 1) WITHOUT RECOVERY TO A \leq GRADE 1 OR BASELINE STATUS WOULD RESULT IN TAKING THE PATIENT OFF TREATMENT.

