7.2.1.1 Adverse Event Description and Grade

The descriptions and grading in the NCI CTCAE version 5.0 will be used in the reporting of AEs. A change in grade will be reported as a separate AE. A copy of the CTCAE v 5.0 may be downloaded from

http://ctep.cancer.gov/protocolDevelopment/electronic_applications/ctc.htm.

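### The DLT definition stops at Grade 3 for hemolysis and at Grade 4 for nonhematological, non-CNS toxicity, so some of the most severe events are not counted as written

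*Protocol*

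**What the plan says.** Section 4.1.1 defines DLTs in three groups.

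- **Hematological.** The items include "Grade 3 hemolysis", "Grade 4 anemia", laboratory limits for neutrophils and platelets, febrile neutropenia, and a catch-all that begins "Any hematological toxicity that prevents administration of" and continues with at least 80% of the planned LC dose.
- **CNS.** One item is "Grade 2 CNS ischemia", preceded by a greater-than-or-equal sign. Another is "Symptomatic CNS hemorrhage of any grade". Neurological toxicity also starts at Grade 2 or above, with conditions on daily activities and resolution.
- **Nonhematological, non-CNS.** "Grade 3 and 4 nonhematological, non-CNS toxicities will be considered DLTs, with the following exceptions". The exceptions include "A first episode of deep venous thrombosis (DVT) or pulmonary embolism", with no grade attached. Separate hepatic items use transaminase and bilirubin limits.

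Section 7.2.1.1 sets the grading scale: "The descriptions and grading in the NCI CTCAE version 5.0 will be used in the reporting of AEs". It also has each change of grade reported as a separate event. Table 3 makes the number of DLTs under Section 4.1.1 the primary endpoint, and Table 10 uses that number to direct dose assignment.

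Under Sections 4.1 and 4.1.5 and Table 9, a patient without a DLT is evaluable only after receiving 80% of LC, 80% of radiotherapy and 60% of temozolomide in the first 10 weeks.

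**The concern.** Two items in the definition of the primary endpoint give closed grades, while the CNS items in the same section are open upward. Anyone applying the list as written would count a Grade 3 event but could leave out a worse event of the same kind.

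Hemolysis matters here. Section 2.2.3 reports severe hemolysis in dogs at 20 mg/kg, with two deaths in that group. Section 2.2.1 equates that dose to 400 mg/m², which is nominally Level 3 in Table 4. Section 7.1.4.4 adds monitoring because hemolytic anemia has been described. With cohorts of 3, one event is enough to change a dose assignment, so whether it counts should not depend on someone reading past the text.

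**Working it through.** **1. Does bare Grade 3 mean Grade 3 or worse?** Section 4.1.1 uses three styles:
- open upward, in the CNS items;
- both grades named, for lymphopenia, hypophosphatemia and alkaline phosphatase;
- bare Grade 3, for hemolysis and for exceptions such as fatigue and hyperglycemia.

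In the exceptions, bare Grade 3 has to mean exactly Grade 3, or Grade 4 fatigue would be exempt too. Reading the hemolysis item as open would give the same words two meanings in one section. No other section adds Grade 5 or death to the DLT list.

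**2. What do the other items still catch?**

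| Event | Counted as a DLT? |
|---|---|
| Fatal CNS ischemia or symptomatic CNS hemorrhage | Yes, open upward |
| Fatal event crossing a neutrophil, platelet or hepatic limit, or with febrile neutropenia | Yes, whatever the outcome |
| Grade 4 hemolysis with Grade 4 anemia | Yes, through the anemia item |
| Grade 4 hemolysis that prevents 80% of planned LC | Yes, through the catch-all |
| Event recorded at a named grade before it worsened | Yes, the earlier record qualifies |
| Other Grade 4 hemolysis | Not named |
| Other fatal nonhematological, non-CNS toxicity | Not named |

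**3. When does the catch-all stop helping?** Section 4.1.5 equates 80% of LC with 8 of 10 doses. The Schedule of Activities places the eighth dose on Day 50. With doses on schedule, hemolysis arising after that dose cannot prevent 80% of planned LC.

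- Days 50 to 70 are 21 of the 70 days in the window.
- The last third lasts 70/3 = 23.3 days, and Section 8.4.8 gives it 50% of the DLT risk.
- If risk is even within that third (my assumption), Days 50 to 70 carry 21/23.3 × 50% = 45% of the assumed DLT risk.

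This is the design's assumption for all DLTs, not an estimate for hemolysis. Radiotherapy and concurrent temozolomide are scheduled for Weeks 1 to 6. Such a patient would therefore normally be evaluable and stay in the denominator.

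**4. Reproducing the decision boundaries.** Section 8.4.8 gives a 30% target and an interval of 23.6% to 35.9%. The inner limits are not stated; I assume the usual p1 = 0.6 × 0.30 = 0.18 and p2 = 1.4 × 0.30 = 0.42.

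- λe = ln(0.82/0.70) / ln[(0.30 × 0.82)/(0.18 × 0.70)] = 0.2365
- λd = ln(0.70/0.58) / ln[(0.42 × 0.70)/(0.30 × 0.58)] = 0.3585

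Both match the protocol within rounding, and the complete-data decisions agree with Table 10.

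**5. Effect of one uncounted event, patient evaluable and none pending (Table 10).**

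| Evaluable | All events counted | One event not counted |
|---|---|---|
| 3 | 1: stay | 0: escalate |
| 3 | 2: de-escalate | 1: stay |
| 3 | 3: de-escalate and eliminate | 2: de-escalate |
| 6 | 2: stay | 1: escalate |
| 6 | 3: de-escalate | 2: stay |
| 6 | 4: de-escalate and eliminate | 3: de-escalate |

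**6. Death before the exposure thresholds are met.** Such a patient has no DLT as written and is not evaluable. Table 10 counts evaluable patients, so the patient leaves both numerator and denominator. A cohort of 3 then has 2 evaluable patients, and Table 10 has no row for 2.

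**7. The thromboembolism exception.** A fatal first pulmonary embolism lies outside the general rule as worded. If that rule were opened upward, the ungraded exception would still exempt it.

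**The case against.** The strongest reply is that the gap is small and nobody would apply it. Much of this stands.

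- A reader might infer that fatal toxicity in general is not dose limiting. The protocol does not support that, because fatal CNS events and events crossing the laboratory limits count.
- A reader might infer that every Grade 4 hemolysis is missed. That is also wrong, given the anemia item, the 80% catch-all and the separate reporting of grade changes.
- The DLT count is not the only input. Section 4.1.2 adds patients treated and pending, Section 8.4.9 adds weighted follow-up time, and Section 5.10 has the Safety Review Committee (SRC) weigh safety and tolerability. Section 4.1.6 requires SRC sign-off before a new dose cohort.
- Mixed style points to loose drafting more than to a deliberate ceiling. "Grade 4 anemia" is closed as well.

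Oversight does not close the gap, however. In Section 5.10, the halt for a repeated serious event needs the same event in more than 2 patients of a cohort. The halt for unacceptable toxicity is optional and rests on the investigator's opinion. Neither makes the event a DLT for the primary endpoint or for Table 10.

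**Conclusion.** The point holds in a limited form. As written, the uncounted events are Grade 4 hemolysis that meets no other item, and fatal nonhematological, non-CNS toxicity outside the hepatic limits that was not first recorded at Grade 3 or 4. The separate-record rule narrows the hemolysis group in the same way.

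The size is one decision step in Table 10 for each uncounted event in the rows shown, provided the patient has met the exposure thresholds. It would be tempting to say that any such death yields 0 of 3. The evaluability rules do not support that for an early death, which removes the patient from the count instead.

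The conclusion rests on a literal reading, on-schedule dosing for the Day 50 example, and complete data for the Table 10 steps. Taking Grade 5 as death is the usual CTCAE convention, which the protocol does not spell out. Little depends on it, since neither term appears in the DLT definition. The probable cause is a drafting slip, but it sits in the definition of the primary endpoint and should be corrected.

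**What to change.** Reconcile the grade wording of the hemolysis item and the nonhematological, non-CNS rule with the CNS items, or state why an upper limit is intended. State how a death within the 10-week window is classified, both for DLT counting and for evaluability, and say whether the thromboembolism exception applies whatever the outcome.

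The choice of grades belongs to the sponsor and investigators. Section 4.1.1 uses the same definition to decide when a patient comes off treatment, so any change must be checked against those rules too. The cost is a few words in Section 4.1.1 and a sentence on deaths there and in Table 9. The design and sample size do not change.

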For patients receiving concurrent TMZ and LC, blood counts will be evaluated weekly. Within -5 days (5 days prior to) the first dose of each 5-day TMZ treatment, the patient must have an ANC $\geq 1500/\mu\text{L}$ and platelet count $\geq 100,000/\mu\text{L}$. On Day 1 of each cycle (within -5 days) all nonhematological Grade 3 or 4 toxicities (except for alopecia, nausea and vomiting, and lymphopenia), that is definitely, probably, or possibly related to TMZ must have resolved (Common Terminology Criteria for Adverse Events [CTCAE] Grade ≤ 1). If toxicity persists, treatment should be delayed by 1 week for up to 3 consecutive weeks. If after 3 weeks of delay all toxicity has still not resolved, any further adjuvant treatment with TMZ should be stopped.

5.5.4 *Radiotherapy*

No specific prophylaxis is indicated for the RT regimen. The Investigator may use low-dose benzodiazepines if clinically indicated for anxiolytic management if compliance is an issue.

Modalities: Only conformal techniques (3-dimensional conformal radiotherapy [3D CRT] or intensity-modulated radiotherapy [IMRT]) will be allowed in this study. Proton radiotherapy is not allowed. Two-dimensional techniques not employing volumetric target volume definition or 3-dimensional assessments of radiation dose are not allowed. The radiation technology utilized as well as the dosing and target volumes are determined according to current standard of care and described below. In most circumstances IMRT will be optimal as most target volumes are convex or concave, such that there would likely be an advantage in protection of critical structures and brain.

Equipment: All patients must be treated with a linear accelerator with nominal photon energy between 6 to 18 MV. Co-60 is not allowed on this study. Electrons and protons may not be used.

Additional information on treatment planning may be found in [Section 9.2](#) (Appendix 2).

5.5.4.1 *Potential Toxicity of Radiotherapy*

Side effects of radiation may occur in an increased frequency and severity when receiving LC along with standard RT and TMZ.

The following side effects may be associated with RT for brain cancer:

Likely:

- Tiredness including mental slowing
- Lack of energy
- Redness or soreness of scalp
- Hair loss (temporary or permanent)
- Short-term hearing loss
- Possible increase in brain tumor symptoms such as headaches, seizures, or weakness during treatment
- Edema or swelling of the brain that may require steroid medication

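### For a DLT-type, TMZ-related toxicity in the adjuvant phase, Sections 4.1.1 and 5.5.3 give contradictory instructions for delays of more than 14 and up to 21 days, and leave unclear which agents stop after that

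*Protocol*

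**What the plan says.** Protocol Section 4.1.1 closes its list of dose-limiting toxicities with a rule for patients on adjuvant treatment. It applies to any adverse event of the kind defined there as a DLT, "CAUSING DELAY IN TREATMENT OF OVER 14 DAYS (POST CYCLE 1 DAY 1) WITHOUT RECOVERY TO A" Grade 1 or lower. The consequence follows: "GRADE 1 OR BASELINE STATUS WOULD RESULT IN TAKING THE PATIENT OFF TREATMENT". The rule does not say whether treatment means LC, TMZ or both.

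Protocol Section 5.5.3 sets conditions for starting each TMZ cycle. Nonhematological Grade 3 or 4 toxicity at least possibly related to TMZ must have come down to Grade 1 or lower, apart from a few named exceptions. The section continues: "If toxicity persists, treatment should be delayed by 1 week for up to 3 consecutive weeks". It then says: "If after 3 weeks of delay all toxicity has still not resolved, any further adjuvant treatment with TMZ should be stopped". It does not mention LC at this point.

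Under Section 4.1.3 and Table 7, adjuvant treatment is weekly LC plus TMZ for up to six 4-week cycles.

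**The concern.** A rule that ends a patient's treatment should give one answer wherever it is read. Here an investigator holding a cycle for a TMZ-related toxicity finds one time limit in the DLT section and a longer one in the TMZ section. The consequences are also described differently.

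The choice of section would decide how much adjuvant LC and TMZ the patient receives, when End of Treatment falls, and whether the patient is counted as discontinued for toxicity. Sections 8.4.1 and 8.4.3 summarize discontinuation reasons and exposure, and tolerability with adjuvant TMZ is among the stated objectives. Two patients with the same course could be managed and reported differently. A statistical analysis plan cannot repair this, because the rule acts at the site.

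**Working it through.** No sample size, power or error rate is involved. The check sets the two rules side by side and looks for anything that reconciles them.

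**1. Do the rules cover the same events?** In part.

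- Section 4.1.1 counts Grade 3 and 4 nonhematological, non-CNS toxicity as DLTs, with exceptions, whatever the cause.
- Section 5.5.3 requires at least a possible relation to TMZ and has its own exceptions.
- Section 5.5.2.6 lists rash as a known TMZ toxicity, and rash is in neither list of exceptions. A Grade 3 rash judged possibly TMZ-related therefore falls under both rules.
- The paragraph in Section 5.5.3 opens "For patients receiving concurrent TMZ and LC, blood counts will be evaluated weekly", so it is not confined to patients who have left LC.

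Hematological events are left aside, because Section 5.5.3 does not say plainly whether its delay sentence also covers the blood-count criteria.

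**2. What does each rule require over time?** The Section 5.5.3 limit is 3 × 7 = 21 days. The Section 4.1.1 limit is passed on day 15. For an unresolved event meeting both rules:

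| Delay | Section 4.1.1 | Section 5.5.3 | Consistent? |
|---|---|---|---|
| Up to 14 days | No stop | First and second weekly delays | Yes |
| Days 15 to 21 | Off treatment | Third weekly delay, then resumption if resolved | No |
| Beyond 21 days | Off treatment, agents not named | TMZ stopped, LC not mentioned | Unclear for LC |

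The window of direct contradiction is 21 − 14 = 7 days.

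**3. Example.** A Grade 3 TMZ-related rash is present at planned Cycle 2 Day 1 and resolves to Grade 1 on day 18. Under Section 4.1.1 the patient has been off treatment since day 15. Under Section 5.5.3 the patient may start Cycle 2.

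**4. Recovery standard.** Section 4.1.1 accepts Grade 1 or lower, or baseline. Section 5.5.3 accepts only Grade 1 or lower. An event that returns to a baseline above Grade 1 has recovered under the first rule but not under the second.

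**5. Is there a reconciling rule?** Sections 4.1.2 and 5.5.3 both refer to Section 5.10 for adjustments. Section 5.10 deals with dose levels, the maximum LC dose, cohort expansion and safety halts. It sets no limit on delay for an individual patient. Section 6.1 sets none either. No section says which rule prevails.

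**6. Largest effect for one patient.** Planned weekly LC infusions are 6 + 4 = 10 before the adjuvant phase and 6 × 4 = 24 within it, 34 in all. If treatment ends at the start of Cycle 2 and off treatment is taken to include LC, up to 5 × 4 = 20 of the 34 infusions and 5 of the 6 adjuvant TMZ cycles are lost. Twenty is an upper bound, and the loss is smaller if LC was infused during the delay.

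**The case against.** The strongest reply is that the rules have different jobs. Section 4.1.1 deals with DLT-type events of any cause, and Section 5.5.3 decides whether a TMZ cycle may start. The 3 weeks can be read as a general ceiling, with 14 days as a tighter limit for the DLT-type subset. That reading is possible, but the protocol does not state it, and for events meeting both rules it would empty the third week of meaning. Assigning Section 4.1.1 to LC and Section 5.5.3 to TMZ also lacks support, since Section 4.1.1 speaks only of treatment.

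The objection does limit the reach of the point. Four stronger conclusions that a reader might infer are not supported:

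- **That the rules clash for every unresolved delay of 15 to 21 days.** Grade 3 fatigue is excluded as a DLT. An ANC of 1000/µL misses the cycle-start requirement of 1500/µL but is well above the DLT cut-off of 500/µL. It would not trigger Section 4.1.1 unless it also prevented 80% of planned LC. DLT-type events unrelated to TMZ fall under Section 4.1.1 alone.
- **That Section 5.5.3 keeps the patient on LC, or costs no infusions.** It says nothing about LC, and Section 4.1.3 caps adjuvant LC at 24 weeks, so a delay may itself cost doses.
- **That adverse-event collection depends only on the last LC dose.** Section 6.1 also names the last TMZ dose.
- **That the two sites would produce differing PFS or OS.** The study is at a single institution with shared safety oversight, efficacy is descriptive, no site comparison is planned, and PFS and OS follow-up continue after LC stops.

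**Conclusion.** The contradiction stands for a defined set of patients: those in the adjuvant phase with a nonhematological Grade 3 or 4 toxicity that meets the Section 4.1.1 DLT definition, is at least possibly TMZ-related, and is unresolved after more than 14 and up to 21 days. For them, one section ends treatment and the other permits delay and resumption. Beyond 21 days the defect is an ambiguity about which agents stop, and it should not be described as a conflict over LC.

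For a single patient the consequence can be large, up to the bound worked out above. The documents give no frequency for such events, so the effect across the trial cannot be sized, and any effect on PFS or OS is unquantified. A reader might also fear for the dose-finding result. That does not follow, because the DLT window is the 10 weeks before the adjuvant phase, so TITE-BOIN decisions and the MTD are untouched.

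The conclusion rests on reading treatment in Section 4.1.1 as including adjuvant TMZ, which is the plain sense of the text. It takes no view on which limit is right.

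**What to change.** Reconcile Sections 4.1.1 and 5.5.3 into one adjuvant-phase delay rule. It should state:

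- one maximum delay;
- one recovery standard;
- which agents stop when the limit is passed (LC, TMZ or both).

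Put the rule in one section and cross-refer from the other. If the sponsor intends different limits for different classes of event, the rule should define the classes and say which limit prevails when an event belongs to both. The limits themselves are for the sponsor and investigators to decide. The cost is wording in a protocol amendment, with no extra patients, visits or procedures.
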